7.1 Demographic Data

At the Screening Visit (V0), subject demographic data will be collected. These data include age and gender.

7.2 Medical History

At the Screening Visit (V0), a medical history will be obtained from each subject. Medical history includes a detailed history of prior cosmetic procedures, with start and stop dates, if applicable, as well as any discontinuations due to intolerability or toxicity.

7.3 Concomitant Medications

Therapy considered necessary for the subject's welfare may be given at the discretion of the investigator, including but not limited to medications for other conditions (ie, hypertension, diabetes, etc.), treatment of AEs, estrogens, androgens, anti-androgenic agents, vitamins, iron supplements, folate, and herbal supplements. Medications should be taken consistently throughout the study and at the investigator's discretion.

Concomitant medications as defined for this study include dietary supplements, over-the-counter medications, and oral herbal preparations, as well as changes in dosages of current prescription medications. Concomitant medications will be documented for each subject at each scheduled visit. A detailed history of medications will be documented at screening. Subsequently, at each study visit, subjects will be asked what medication, if any, they have taken since the previous visit. All concomitant medications will be recorded on electronic case report forms (eCRFs).

7.4 Pregnancy

Women of childbearing potential must have a negative urine pregnancy test before any injections or other treatments are given. A reliable method of contraception must be practiced throughout the study. Women of childbearing potential comprises women who have experienced menarche and who have not undergone successful surgical sterilization (hysterectomy, bilateral salpingectomy, or bilateral oophorectomy) or who are not post-menopausal.

7.5 Clinical Scales for Treatment Inclusion Only

- Investigator's assessment of the severity of GLs at maximum frown using the FWS with photonic guide ([REDACTED])
- Investigator's assessment of the severity of CFLs at maximum smile using the FWS with photonic guide ([REDACTED])
- Investigator's assessment of the severity of FHLs at maximum eyebrow elevation using the FWS with photonic guide ([REDACTED])

- Investigator's assessment of the subject's facial photodamage severity using the 10-point SOPS ([REDACTED])
- Investigator's assessment of the subject's SMF using the 5-point SMFRS ([REDACTED])
- Subject's assessment of self-appearance using the 7-point SSRS ([REDACTED])

7.6 Efficacy Endpoint Measurements

7.6.1 FACE-Q

- Subject's assessment overall facial appearance as measured by the FACE-Q Satisfaction with Facial Appearance Scale ([REDACTED])
- Subject's assessment of expectations of life change as measured by the FACE-Q Expectations Scale ([REDACTED])
- Subject's assessment of age-related facial appearance as measured by the FACE-Q Aging Appraisal ([REDACTED])
- Subject's assessment of psychological well-being as measured by the FACE-Q Psychological Function Scale ([REDACTED])
- Subject's assessment of social function as measured by the FACE-Q Social Function Scale ([REDACTED])
- Subject's assessment of overall satisfaction with skin as measured by the FACE-Q Satisfaction with Skin Questionnaire ([REDACTED])

7.6.2 Self-Perception of Age Questionnaire

[figure not shown]
- Subject's assessment of age-related facial appearance as measured by the SPA Questionnaire ([REDACTED])

7.6.3 Global Aesthetic Improvement Scale

- Investigator's assessment of global facial aesthetic improvement as measured by the 5-point GAIS ([REDACTED])
- Subject's assessment of global facial aesthetic improvement as measured by the 5-point GAIS ([REDACTED])

7.6.4 Periorbital Aesthetic Appearance Questionnaire

- Subject's assessment of periorbital area as measured by the PAAQ ([REDACTED])

8 Discontinuation Criteria

8.1 Early Discontinuation of the Study

An investigator may stop the study at his/her study site at any time. Allergan, as the sponsor, may discontinue the study (and/or participation of a single study site) for any reason with appropriate notification. If conditions arise during the study that indicate that the study or an investigational site should be terminated, Allergan, the investigator, the study monitor, REB, and/or regulatory agencies will take appropriate action after consultation. Conditions that may warrant termination of the study or investigational site include, but are not limited to:

- Discovery of an unexpected, serious, or unacceptable risk to subjects enrolled in the study
- The decision on the part of Allergan to suspend or discontinue testing or evaluation of the study treatment
- Failure of an investigator to comply with pertinent national or state regulations, REB-imposed conditions, or protocol requirements
- Submission of knowingly false information to Allergan, study monitor, the REB, or any regulatory agency by the investigator

If the study is prematurely terminated or suspended due to safety issues, Allergan will inform all investigators and applicable regulatory authorities of the termination or suspension and the reason(s) for the termination or suspension. The REB is also to be informed promptly and provided the reason(s) for the termination or suspension by Allergan or by the investigator, as specified by the applicable regulatory requirements. If a premature termination or suspension occurs, Allergan shall remain responsible for providing resources to fulfill the protocol obligations and existing agreements for follow-up of subjects enrolled in the study, and each investigator or authorized designee will promptly inform enrolled subjects, if applicable.

8.2 Early Discontinuation of Individual Subjects

A subject may voluntarily withdraw from the study at any time. Notification of early subject discontinuation from the study and the reason for discontinuation will be made to Allergan and will be clearly documented on the appropriate eCRF. In the event of subject discontinuation, every effort should be made to have the subject complete the primary endpoint FACE-Q Satisfaction with Facial Appearance Overall questionnaire.

It is the right and responsibility of the investigator to discontinue a subject's participation when the subject's health or well-being is threatened by continuation in the study. In the event of premature discontinuation, the investigator should determine the primary reason for discontinuation.

A subject who is withdrawn from the study prior to initiation of treatment may be replaced. Discontinued subjects will not be replaced.

The following are circumstances that could result in a subject's discontinuation from the study:

- AEs or SAEs that render the subject unable to continue study participation
- Protocol violation
- Subject voluntarily withdraws consent
- Non-compliance with study requirements
- Discretion of investigator (must document reason on eCRF)
- Progressive injury (at the discretion of the investigator)
- Changes in the subject's condition that render the subject unacceptable for further participation, in the judgment of the investigator
- Pregnancy (required discontinuation)
- Lost to follow-up
- Unable to physically or mentally tolerate the use of the test treatment
- Exclusion criterion met

9 Treatments

The study treatments are:

- BOTOX Cosmetic
- BELKYRA
- JUVÉDERM VOLITE, JUVÉDERM VOLBELLA with Lidocaine, JUVÉDERM VOLIFT with Lidocaine, and/or JUVÉDERM VOLUMA with Lidocaine
- SkinMedica products

All study drugs/devices must be stored in a secure area, accessible only to study personnel. Allergan will provide each study site with sufficient study treatments (study drugs, devices and SkinMedica) for all study subjects, including back-up study treatments.

Allergan will provide the most recent country-specific Directions for Use and Product Monographs for each product to each investigator to be used in study treatment. Details of formulation, storage, and handling, and complete instructions for administration of treatments can be found in the respective product information for each study drug/device.

All unused study treatments should be retained for return to Allergan.

All products will be used as per their license only. Further details on the products can also be found in the currently approved Directions for Use and Product Monographs.

9.1 Rescue Medications and Concomitant Treatments

No product licensed in Canada is approved as a rescue medication. Administration of hyaluronidase is considered to be “off-label” and has not been provided as a part of the study regimen and should only be used if in the investigator’s judgment it is deemed to be necessary to inject hyaluronidase for the safety of the subject, then the investigator may inject at his/her discretion as a concomitant medication, capturing relevant information.

9.2 Treatment Compliance

The investigator is responsible for compliance with the protocol at the investigational site. The investigator is also responsible for reporting all issues of protocol non-compliance to the respective REB and to Allergan. A representative of Allergan will make frequent contact with the investigator and his/her research staff and will conduct regular monitoring visits at the site to review subject and study drug and device accountability records for compliance with the protocol, eg, subject eligibility criteria, volume of product injected, procedures performed, and follow-up visit schedule.

10 Adverse Events

Throughout the course of the study (from the date of informed consent), all AEs will be monitored and recorded on the AE eCRF. If an AE occurs, the first concern will be the safety of the study participant. All AEs related to study treatments or procedures will be followed until resolved or stabilized or until follow-up is no longer possible.

10.1 Drug

An AE from a drug is defined as any undesired medical occurrence in a subject receiving a pharmaceutical product and which does not necessarily have a causal relationship with this treatment. An AE can therefore be any unfavorable sign and unintended sign (including an abnormal laboratory finding), symptom, or disease temporarily associated with the use of a medicinal (investigational) product, whether or not related to the medicinal (investigational) product.

Adverse events will be assessed and documented, as appropriate, throughout the study (ie, after informed consent has been obtained). At each visit, the investigator will begin by querying for AEs by asking each subject a general, non-directed question such as “How have you been feeling since the last visit?” Directed questioning and examination will then be done as appropriate. All reported AEs will be documented on the AE eCRF.

The daily skin care products (SkinMedica) utilized by subjects are not considered to be investigational products in this study. SkinMedica-related AEs will be handled per SkinMedica Standard Operating Procedures for Postmarketing Safety.

10.2 Medical Device

An AE from a medical device is defined as any undesirable physical, psychological or behavioral effect experienced by a subject during his/her participation in a study, in conjunction with the use of the device, whether or not it is considered related to the procedure or the product. Adverse events may include, but are not limited to, subjective or objective symptoms spontaneously offered by the subject, solicited via subject interviews, uncovered by review of concomitant medications, therapies, and treatments, and/or observed by the investigator. The investigator will record the description (sign, symptom and diagnosis), location, onset, resolution, seriousness, severity, cause, and action taken for any event on the AE eCRF.

Disease signs and symptoms that existed prior to the study injections are not considered AEs unless the condition recurs after the subject has recovered from the pre-existing condition or the condition worsens in intensity or frequency during the study.

10.3 Injection Site Reactions

Injection site reactions following treatment with dermal fillers include redness, pain after injection, tenderness to touch, firmness, swelling, lumps/bumps, bruising, itching, discoloration, and other. Subjects will maintain a diary record of the presence, location, frequency, severity, and duration of any ISR for 30 days after each filler treatment.

Subjects will indicate the occurrence of an ISR and severity (none, mild, moderate, severe) of the event. NOTE: ISRs that persist longer than 30 days be recorded and followed to resolution on the AE eCRF. If an ISR is ongoing or appears 30 days after the subject's last study visit, it will be followed up by Allergan Product Surveillance separate from this study protocol.

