4.3 Safety

All adverse events (AEs) including injection site reactions (ISRs) will be collected from when the ICF is signed through to the last study visit (V12). Serious adverse events (SAEs) will be reported within the specified time and format directly to Allergan and SkinMedica as described in Section 10.8.1.

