10.7 Assessment of Adverse Events

10.7.1 Severity

Assessment of severity of an AE will be rated according to the definitions in Table 10.1 and the worst grade documented. The investigator will review these definitions with the subject for use when completing the subject diary. For events reported on the AE eCRF, eg, ISRs that persist beyond the diary period and other AEs, the investigator will determine the severity classification based on these definitions, his/her experience in the use of dermal fillers and/or the subject's description of the event.

The term "severe" is used to describe the intensity of an AE; the event itself could be of relatively minor clinical significance (eg, "severe headache"). This is not the same as "serious." Seriousness of AEs is based on the outcome of an AE and usually associated with events that pose a threat to a subject's life or functioning.

Table 10.1 Classification of Adverse Events by Intensity

Grade 1 (Mild)	The symptom is barely noticeable to the study subject and does not influence performance or functioning. Concomitant medication is not ordinarily indicated for relief of mild AEs.
Grade 2 (Moderate)	The symptom is of sufficient severity to make the study subject uncomfortable and to influence performance of daily activities. Concomitant medication may be indicated for relief of moderate AEs.
Grade 3 (Severe)	The symptom causes severe discomfort, sometimes of such severity that the study subject cannot continue in the study. Daily activities are significantly impaired or prevented by the symptom. Concomitant medication may be indicated for relief of severe AEs.
Not applicable	In some cases, an AE/ISR may be an “all-or-nothing” finding that cannot be graded.

Abbreviations: AE = adverse event, ISR = injection site reaction.

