11 SAFETY ANALYSES

The safety analysis will be performed using the Full Analysis Population. The safety parameters will include adverse events (AEs). The last nonmissing safety assessment before the first dose of study treatment will be used as the baseline for all analyses of that safety parameter.

Categorical variables will be summarized by number and percentage of patients. No statistical test will be performed.

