11.1 Adverse Events

All Adverse events (AEs) will be classified by Primary System Organ Class (SOC) and Preferred Term (PT) according to the Medical Dictionary for Regulatory Activities (MedDRA) Version 21.0 or newer.

TEAE is defined as an AE that was not present prior to treatment with investigational products but appeared following treatment or was present at treatment initiation but worsened after treatment or become SAE.

An SAE is defined as any AE that either led to death; resulted in a life-threatening illness or injury; resulted in a permanent impairment of a body structure or a body function; required in-patient hospitalization or prolongation of existing hospitalization; resulted in medical or surgical intervention to prevent permanent impairment to body structure or a body function; led to fetal distress, fetal death or a congenital abnormality or birth defect.

AE summary tables will be presented for TEAEs only and will include the following:

- All TEAEs
- TEAEs related to study drug
- TEAEs leading to study discontinuation
- Serious/Severe TEAEs
- Serious/Severe TEAEs related to study drugs
- TEAEs leading to death.

All TEAEs will be summarized by SOC, PT and treatment group using frequency counts and percentages (i.e., number and percentage of subjects with an event). In addition, an overall summary for the categories above will be prepared by treatment group and overall.

All TEAEs will be summarized by SOC, PT, maximum severity, and treatment group using frequency counts and percentages (i.e., number and percentage of subjects with an event)

An AE will be considered as related if the event is Possibly, Probably or Definitely related. If the relationship to study drug is missing, the AE will be treated as related. For AE with severity missing, the missing severity will be imputed as severe.

For the incidence at the subject level by SOC and PT, if a subject experiences more than one event within the same SOC and PT, only one occurrence will be included in the incidence. For the incidence at the subject level by SOC, PT, and severity, if a subject experiences more than one event within the same SOC and PT, only the most severe occurrence will be included in the incidence.

For the incidence at the subject level by SOC, PT, and relationship to investigational product, if a subject experiences more than one event within the same SOC and PT, only the most related occurrence will be included in the incidence.

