17 DATA COLLECTED BUT NOT ANALYZED

This section is not applicable to this study.

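### The protocol conflicts on which form takes a filler injection site reaction of 30 days or less, and the SAP plans no summary of the reaction diary

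*Protocol*

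**What the plan says.** On recording, two sets of protocol text bear on a filler ISR.

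- Protocol 10.3 sets up the diary: "Subjects will maintain a diary record of the presence, location, frequency, severity, and duration of any ISR for 30 days after each filler treatment". Its note then says "ISRs that persist longer than 30 days be recorded and followed to resolution on the AE eCRF". Protocol 10.7.1 uses the same division when it explains severity grading: "For events reported on the AE eCRF, eg, ISRs that persist beyond the diary period and other AEs". It also has the investigator go through the severity definitions with the subject for use in the diary.
- Protocol 4.3 counts ISRs among AEs: "All adverse events (AEs) including injection site reactions (ISRs) will be collected from when the ICF is signed through to the last study visit". The opening of Protocol 10 says that "all AEs will be monitored and recorded on the AE eCRF". Protocol 10.1 sends all reported AEs to that form, and 10.2 does the same for any event in conjunction with a device, with no minimum duration. Protocol 6.2.4 has site staff ask about and record ISRs whenever the subject returns, without naming a form.

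On analysis, the only safety measure that SAP 11 names is AEs. SAP 11.1 limits the tables: "AE summary tables will be presented for TEAEs only and will include the following". Six categories follow, none of them for ISRs, and then listings of AEs. Protocol 11.4.4 plans no ISR summary either. On data collected but not analysed, SAP 17 says: "This section is not applicable to this study".

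**The concern.** The diary is a deliberate safety instrument. It has its own reaction list, severity scale and 30-day window after each filler treatment. The SAP defines ISR among its abbreviations and mentions ISR collection in its introduction, but its analysis sections never return to it.

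Two things are at stake. First, if sites follow 10.3, a filler reaction that resolves within the diary period may never reach a safety table, and a reader of the treatment-emergent AE (TEAE) tables would not know it. Second, if some sites follow 10.3 and others follow 4.3 and 10, the TEAE percentages mix two recording rules across six or seven sites. Protocol 2 gives the lack of safety evidence on combined use as part of the rationale for the study, so local reactions to the fillers are results that readers will look for.

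**Working it through.** There is no stated figure to reproduce. The check sets the passages side by side.

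1. **Rule A (Protocol 10.3, 10.7.1).** A filler ISR goes in the diary for 30 days and on the AE form if it lasts longer.
2. **Rule B (Protocol 4.3, opening of 10, 10.1, 10.2).** ISRs are AEs and all AEs go on the AE form, with no duration threshold. The wording of 6.2.4 and 10.7.1, which mention ISRs and then other AEs, also treats an ISR as a kind of AE.
3. **Precedence.** Rule A is the more specific, but 10.3 does not say that shorter ISRs stay off the AE form, and 10.7.1 gives its division as an example. No section says which rule prevails. The conflict is unresolved.
4. **Route to a table.** The TEAE definition in SAP 11.1 would take in a new reaction after filler treatment. Whether it is tabulated therefore depends on whether it was entered as an AE, which is the point in conflict.
5. **Diary analysis.** SAP 11 and 11.1 contain no diary or ISR table or listing. The blacked-out lines in the SAP contents lie under efficacy section 10.3. The safety section shows only 11.1.

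Outcome under each way of working:

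| Recording followed | Filler ISR of 30 days or less in a planned table? | Diary data summarised? |
|---|---|---|
| Rule A | No | No |
| Rule B | Yes, as a TEAE | No; no rule on a reaction held in both diary and AE form |
| Differs by site | At some sites only | No |

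**Size.** Let N be the number of filler-treated subjects, p the share with any filler ISR, and f the share of those with at least one ISR beyond 30 days. Under rule A the AE tables show N × p × f of the N × p affected subjects, so the share absent is 1 − f. Under rule B it is zero by rule. The documents plan N of up to 60 but give neither p nor f. With f anywhere from 0 to 1, the absent share under rule A can lie anywhere from 100% to 0%. No narrower range follows from the documents.

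**The case against.** The strongest reply is that nothing is excluded. Protocol 10.3 never uses the word only, five protocol sections (4.3, 6.2.4, 10, 10.1, 10.2) point towards recording every ISR, and SAP 11 says "The safety parameters will include adverse events (AEs", where include need not mean only. SAP 17 also looks like standard text: SAP 8.5 already says that the inclusion scales will not be reported, so a not-applicable entry says little about the diary. The visit sections and Table 6.1 are not visible and might describe how diary entries are reviewed or transcribed. Neither document states a safety objective.

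Much of this stands. It shows that the loss of short ISRs depends on which rule a site follows. It does not supply an analysis of the diary: a transcription rule in the visit sections would settle recording, but the SAP would still plan no summary of type, location, severity and duration. If SAP 17 is standard text, it is still inaccurate for these data.

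Two stronger readings are tempting and are not supported:

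- A reader might infer that most local filler toxicity is left out, or try to count the lost subjects or diary days. The documents give no incidence or duration. Protocol 6.2.5.2 makes touch-ups at V8 and V9 conditional, and the visit spacing that would show whether diary windows overlap is not visible.
- A reader might infer that the group without BELKYRA will look safer because fillers are its main injectables. Both groups pass through the filler phase from V7 (Protocol 4.1), so a diary rule for fillers reaches both. Protocol 11.1 and SAP 10 also say that the study is not designed to compare the groups.

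**Conclusion.** The point holds as a conflict between recording rules together with a reporting gap. If Protocol 10.3 governs, filler ISRs of 30 days or less enter no planned safety table. Whichever rule governs, the readable SAP plans no summary of the diary, contrary to SAP 17, and sites may handle the same reaction differently.

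The size cannot be stated. It is zero by rule if every ISR goes on the AE form, and otherwise depends on an incidence and a duration distribution that the documents do not give. The conclusion assumes that the blacked-out SAP text holds no diary analysis, which the position of the redacted contents lines supports. The primary efficacy analysis is not affected. The change should be made before database lock, since the SAP is to be final by then (Protocol 11.1). The recording rule needs settling as early as possible, because a later table cannot undo different practice between sites.

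**What to change.** 1. Add to SAP 11 a descriptive diary ISR table on the Full Analysis Population, which the SAP uses for safety. Give the number and percentage of subjects with any ISR and with each type listed in Protocol 10.3, by maximum severity and by duration, after each filler treatment, by group and overall. For touch-ups, use the subjects treated at that session as the denominator.
2. State in SAP 11.1 whether diary ISRs count in the TEAE tables, with a rule that prevents one reaction from being counted twice. Footnote the TEAE tables to match.
3. Reconcile Protocol 10.3 and 10.7.1 with 4.3, 10, 10.1 and 10.2, so that one rule says which form takes a filler ISR of 30 days or less.
4. Correct SAP 17: either the diary is analysed as in step 1, or it is named there as collected but not analysed.

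The cost is one or two extra tables from data already collected and a wording change in both documents. No new subjects, visits or tests are needed. The downside for the sponsor is a reported local reaction rate that may look less favourable.
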